6.7.9. Plasma PK

PK blood sampling will be performed using the site’s local procedures and analyzed at a central laboratory. PK blood samples will be processed, placed in individual tubes, and stored/shipped to the central laboratory as per instructions outlined in the laboratory manual.

Table 6-1. PK Timepoints

	Day 1/Baseline: 2-4 hrs post-dose	Days 7 and 14: pre-dose	Day 21: anytime
PK samples	X	X	X

6.7.10. PPD [Redacted]

PPD [Redacted]

6.7.11. **Optional Extended Viral Monitoring**

PPD [Redacted]

6.7.12. **Optional Registry:**

PPD [Redacted]

- PPD [Redacted]

- PPD [Redacted]

— PPD [Redacted]

— PPD [Redacted]

— PPD [Redacted]

PPD [REDACTED]

- PPD [REDACTED]
- PPD [REDACTED]

Clinical data collection for Optional Registry:

PPD [REDACTED] :

- PPD [REDACTED]
- PPD [REDACTED]
- PPD [REDACTED]
- PPD [REDACTED]
- PPD [REDACTED]
- PPD [REDACTED]

6.7.13. Spirometry

Spirometry testing measurements, obtained by certified respiratory therapists or other nurses/technicians trained in pulmonary function testing, will be obtained at Screening or on Day 1/Baseline and Day 28/End of Study.

The study Day 1/Baseline forced expiratory volume in 1 second (FEV₁) and forced vital capacity (FVC) but must be obtained *prior to IMP administration*. Alternatively, measures of FEV₁ and FVC obtained for the purposes of patient care within 2 days prior to Day 1/Baseline may be used to satisfy the Screening/Day 1/Baseline spirometry measurements. However, these tests must have been obtained at the local site of subject enrollment and the same spirometry machine should be utilized for the Day 28/End of Study measurement.

The Day 28/End of Study spirometry measurements by the certified respiratory therapist do not have to be obtained the same day as the clinic visit, but must be performed within the study visit window (+2 days). Spirometry measures performed as part of standard clinical care within the visit window will be acceptable.

Subjects will also be issued a handheld spirometer for self-administered spirometry testing. These handheld spirometry measures will be obtained by the subject at Days 1/Baseline, 3, 5, 7, 9, 14, 21, and 28/End of Study. Handheld spirometry measures must be obtained in the presence of study staff at Days 1/Baseline and 28/End of Study.

In addition to the study-specific measures described above, all spirometry and other measurements of pulmonary function obtained at unplanned study times, as part of standard clinical care during the study period, will be collected.

Finally, historical spirometry test values will also be collected as follows:

- 1) the average of the 2 highest FEV₁ values and 2 highest PEF_{25%-75%} values measured post-lung transplant, obtained at least 3 weeks apart without the administration of a bronchodilator (the “baseline” values used as a reference point for any future diagnosis of bronchiolitis obliterans syndrome [BOS]), and
- 2) spirometry test values measured within a 3-month period prior to the current active RSV infection. If multiple spirometry measures were obtained over the 3-month interval, the values associated with the test capturing the highest absolute FEV₁ value (in liters) will be collected. If no spirometry tests were collected within the 3-month interval prior to the onset of the current RSV infection (before enrollment into this trial), then the most recent prior spirometry test values will be collected.

7. ADVERSE EVENTS AND TOXICITY MANAGEMENT

7.1. Definitions of Adverse Events, Adverse Reactions, and Serious Adverse Events

7.1.1. Adverse Events

An adverse event (AE) is any untoward medical occurrence in a clinical study subject administered a medicinal product, which does not necessarily have a causal relationship with the treatment. An AE can therefore be any unfavorable and/or unintended sign, symptom, or disease temporally associated with the use of a medicinal product, whether or not considered related to the medicinal product. Adverse events may also include pre- or post-treatment complications that occur as a result of protocol specified procedures, lack of efficacy, overdose, drug abuse/misuse reports, or occupational exposure. Preexisting events that increase in severity or change in nature during or as a consequence of participation in the clinical study will also be considered AEs.

An AE does not include the following:

- Medical or surgical procedures such as surgery, endoscopy, tooth extraction, and transfusion. The condition that led to the procedure may be an adverse event and must be reported.
- Pre-existing diseases, conditions, or laboratory abnormalities present or detected before the Screening visit that do not worsen
- Situations where an untoward medical occurrence has not occurred (eg, hospitalization for elective surgery, social and/or convenience admissions)
- Overdose without clinical sequelae
- Any medical condition or clinically significant laboratory abnormality with an onset date before the consent form is signed and not related to a protocol-associated procedure is not an AE. It is considered to be pre-existing and should be documented on the medical history CRF.

7.1.2. Serious Adverse Events

A **serious adverse event** (SAE) is defined as an event that, at any dose, results in the following:

- Death
- Life-threatening (Note: The term “life-threatening” in the definition of “serious” refers to an event in which the subject was at risk of death at the time of the event; it does not refer to an event that hypothetically might have caused death if it were more severe.)
- In-patient hospitalization or prolongation of existing hospitalization

- Persistent or significant disability/incapacity
- A congenital anomaly/birth defect
- A medically important event or reaction: such events may not be immediately life-threatening or result in death or hospitalization but may jeopardize the subject or may require intervention to prevent one of the other outcomes constituting SAEs. Medical and scientific judgment must be exercised to determine whether such an event is a reportable under expedited reporting rules. Examples of medically important events include intensive treatment in an emergency room or at home for allergic bronchospasm; blood dyscrasias or convulsions that do not result in hospitalization; and development of drug dependency or drug abuse. For the avoidance of doubt, infections resulting from contaminated medicinal product will be considered a medically important event and subject to expedited reporting requirements.

7.1.2.1. Protocol-Specific Serious Adverse Event Instructions

To minimize the possibility of exposing study subjects to unusual risk, the safety information from the study will also be reviewed by an independent DMC on an ongoing basis. The DMC may have access to partially blinded or unblinded data and will determine if it is safe to continue the study according to the protocol.

7.1.3. Clinical Laboratory Abnormalities and Other Abnormal Assessments as Adverse Events or Serious Adverse Events

Laboratory abnormalities without clinical significance are not recorded as AEs or SAEs. However, laboratory abnormalities (eg, clinical chemistry, hematology, and urinalysis) that require medical or surgical intervention or lead to IMP interruption, modification, or discontinuation must be recorded as an AE, as well as an SAE, if applicable. In addition, laboratory or other abnormal assessments (eg, electrocardiogram, x-rays, vital signs) that are associated with signs and/or symptoms must be recorded as an AE or SAE if they meet the definition of an AE or SAE as described in Sections 7.1.1 and 7.1.2. If the laboratory abnormality is part of a syndrome, record the syndrome or diagnosis (eg, anemia), not the laboratory result (ie, decreased hemoglobin).

For specific information on handling of clinical laboratory abnormalities in this study, please refer to Section 7.5.

7.2. Assessment of Adverse Events and Serious Adverse Events

The investigator or a designated qualified sub-investigator is responsible for assessing AEs and SAEs for causality and severity, and for final review and confirmation of accuracy of event information and assessments.

7.2.1. Assessment of Causality for IMP and Procedures

The investigator or a designated qualified sub-investigator is responsible for assessing the relationship to IMP therapy using clinical judgment and the following considerations:

- **No:** Evidence exists that the adverse event has an etiology other than the IMP. For SAEs, an alternative causality must be provided (eg, pre-existing condition, underlying disease, intercurrent illness, or concomitant medication).
- **Yes:** There is reasonable possibility that the event may have been caused by the investigational medicinal product.

It should be emphasized that ineffective treatment should not be considered as causally related in the context of adverse event reporting.

The relationship to study procedures (eg, invasive procedures such as venipuncture or biopsy) should be assessed using the following considerations:

- **No:** Evidence exists that the adverse event has an etiology other than the study procedure.
- **Yes:** The adverse event occurred as a result of protocol procedures, (eg, venipuncture)

7.2.2. Assessment of Severity

Severity should be recorded and graded according to the GSI Grading Scale for Severity of Adverse Events and Laboratory Abnormalities. For AEs or SAEs associated with laboratory abnormalities, the event should be graded on the basis of the clinical severity in the context of the underlying conditions; this may or may not be in agreement with the grading of the laboratory abnormality.

7.3. Investigator Requirements and Instructions for Reporting Adverse Events and Serious Adverse Events to Gilead

Requirements for collection prior to IMP initiation:

After informed consent, but prior to initiation of study medication, the following types of events should be reported on the case report form (eCRF): all SAEs and adverse events related to protocol-mandated procedures.

Adverse Events:

Following initiation of study medication, all AEs, regardless of cause or relationship, through the Day 28/End of Study visit must be reported to the CRF/eCRF database as instructed. All AEs should be followed up until resolution or until the adverse event is stable, if possible.

Gilead Sciences may request that certain AEs be followed beyond the protocol defined follow up period, as determined by the Medical Monitor.

Serious Adverse Events:

All SAEs, regardless of cause or relationship, that occurs after the subject first consents to participate in the study (ie, signing the informed consent) and throughout the duration of the study, including the protocol-required post treatment follow-up period, must be reported to the eCRF database and Gilead Drug Safety and Public Health (DSPH) as instructed. This also includes any SAEs resulting from protocol-associated procedures performed after informed consent is signed.

Any SAEs and deaths that occur, regardless of causality, should also be reported.

Investigators are not obligated to actively seek SAEs after the protocol defined follow up period (the Day 28/End of Study visit), however, if the investigator learns of any SAEs that occur after study participation has concluded and the event is deemed relevant to the use of IMP, he/she should promptly document and report the event to Gilead DSPH.

PPD

All AEs and SAEs will be recorded in the eCRF database within the timelines outlined in the eCRF completion guideline.

Electronic Serious Adverse Event (eSAE) Reporting Process:

- Site personnel record all SAE data in the eCRF database and from there transmit the SAE information to Gilead DSPH within 24 hours of the investigator's knowledge of the event. Detailed instructions can be found in the eCRF completion guidelines.
- If for any reason it is not possible to record the SAE information electronically (ie, the eCRF database is not functioning), record the SAE on the paper serious adverse event reporting form and submit within 24 hours to:

Gilead DSPH:	[contact]
	E-mail:	[contact]

- As soon as it is possible to do so, any SAE reported via paper must be transcribed into the eCRF Database according to instructions in the eCRF completion guidelines.
- If an SAE has been reported via a paper form because the eCRF database has been locked, no further action is necessary.
- For fatal or life-threatening events, copies of hospital case reports, autopsy reports, and other documents are also to be submitted by e-mail or fax when requested and applicable. Transmission of such documents should occur without personal subject identification, maintaining the traceability of a document to the subject identifiers.

- Additional information may be requested to ensure the timely completion of accurate safety reports.
- Any medications necessary for treatment of the SAE must be recorded onto the concomitant medication section of the subject's eCRF and the event description section of the SAE form.
- Site personnel should record all SAE data in the eCRF database for those protocol-specific SAEs which are exempted from expedited reporting requirements (Section 7.1.2.1). They should also transmit the SAE information to Gilead DSPH if the SAEs are assessed by the investigator as related to the IMP or study procedure.

7.4. Gilead Reporting Requirements

Depending on relevant local legislation or regulations, including the applicable US FDA Code of Federal Regulations, the EU Clinical Trials Directive (2001/20/EC) and relevant updates, and other country-specific legislation or regulations, Gilead may be required to expedite to worldwide regulatory agencies reports of SAEs, serious adverse drug reactions (SADRs), or suspected unexpected serious adverse reactions (SUSARs). In accordance with the EU Clinical Trials Directive (2001/20/EC), Gilead or a specified designee will notify worldwide regulatory agencies and the relevant Independent Ethics Committee (IEC) in concerned Member States of applicable SUSARs as outlined in current regulations.

Assessment of expectedness for SAEs will be determined by Gilead using reference safety information specified in the current presatovir (GS-5806) IB or relevant local label as applicable.

All investigators will receive a safety letter notifying them of relevant SUSAR reports associated with any study IMP. The investigator should notify the IRB or IEC of SUSAR reports as soon as is practical, where this is required by local regulatory agencies, and in accordance with the local institutional policy.

7.5. Clinical Laboratory Abnormalities and Other Abnormal Assessments as Adverse Events or Serious Adverse Events

Laboratory abnormalities are usually not recorded as AEs or SAEs. However, laboratory abnormalities (eg, clinical chemistry, hematology) independent of the underlying medical condition that require medical or surgical intervention or lead to IMP interruption or discontinuation must be recorded as an AE, as well as an SAE, if applicable. In addition, laboratory or other abnormal assessments (eg, vital signs) that are associated with signs and/or symptoms must be recorded as an AE or SAE if they meet the definition of an AE or SAE, respectively, as described in Section 7.1. If the laboratory abnormality is part of a syndrome, record the syndrome or diagnosis (ie, anemia) not the laboratory result (ie, decreased hemoglobin).

Severity should be recorded and graded according to the GSI Grading Scale for Severity of Adverse Events and Laboratory Abnormalities [Appendix 5](#). For AEs or SAEs associated with laboratory abnormalities, the event should be graded on the basis of the clinical severity in the context of the underlying conditions; this may or may not be in agreement with the grading of the laboratory abnormality.

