8.7.1. Adverse Events

Clinical and laboratory adverse events will be coded using the Medical Dictionary for Regulatory Activities (MedDRA). System Organ Class (SOC), High-Level Group Term (HLGT), High-Level Term (HLT), Preferred Term (PT), and Lower-Level Term (LLT) will be attached to the clinical database.

Events will be summarized on the basis of the date of onset for the event. A treatment-emergent adverse event will be defined as any adverse event that begins on or after the date of first dose of IMP up to Day 28, or any AEs leading to premature discontinuation of IMP.

Summaries (number and percentage of subjects) of treatment-emergent adverse events (by SOC, and PT) will be provided by treatment group.

AEs will also be summarized by relationship to treatment (IMP) and severity.

A listing of AEs will be provided for all subjects who experience an SAE. Data listings will also be provided for subjects who discontinued the study due to any AE, as well as for an SAE.

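### Protocol 7.1.3 and 7.5 set different rules for when a laboratory abnormality must be recorded as an AE, so some laboratory-driven interventions and drug stops can be missing from the AE tables

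*Protocol*

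**What the plan says.** Two protocol sections with the same title cover laboratory abnormalities as AEs.

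- **Section 7.1.3** starts from clinical significance: "Laboratory abnormalities without clinical significance are not recorded as AEs or SAEs". It then makes recording mandatory for abnormalities "that require medical or surgical intervention or lead to IMP interruption, modification, or discontinuation must be recorded as an AE". No condition is placed on cause. It ends with a hand-off: "For specific information on handling of clinical laboratory abnormalities in this study, please refer to Section 7.5".
- **Section 7.5** starts from a broader default: "Laboratory abnormalities are usually not recorded as AEs or SAEs". Its mandatory trigger covers only abnormalities "independent of the underlying medical condition that require medical or surgical intervention or lead to IMP interruption or discontinuation must be recorded as an AE".

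Both sections also require recording when an abnormality comes with signs or symptoms and meets the AE definition.

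Three other protocol provisions bear on this. Section 7.1.1 counts as AEs "Preexisting events that increase in severity or change in nature during or as a consequence of participation in the clinical study". Section 7.3 asks for every AE after the first dose through Day 28, whatever its cause, and for every SAE from consent onward on the same basis. Section 7.2.1 makes the investigator "responsible for assessing the relationship to IMP therapy using clinical judgment".

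On the analysis side, Protocol 8.7.1 defines treatment-emergent events by onset date, "or any AEs leading to premature discontinuation of IMP". SAP 7.1.5.1 follows this, and SAP 7.1.6 tabulates treatment-emergent AEs leading to premature discontinuation of study drug. All of these start from an AE record.

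**The concern.** A site that follows 7.5 has to decide whether an abnormality is due to the underlying condition before it knows whether an AE record is required. A site that follows 7.1.3 does not. The same finding can therefore be an AE at one centre and only a laboratory value at another.

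Subjects here are lung transplant recipients with an acute viral infection, so attribution to the underlying condition is open to an investigator in a way it would not be in healthy volunteers. Laboratory values can also end treatment: Protocol 3.5 lists ALT or AST above 5 times the upper limit of normal as a reason for potential discontinuation of study drug, separate from its criterion for Grade 3 or 4 AEs. If such a stop has no AE record, it is absent from the table a reader would consult to see how many subjects stopped for an adverse event, and it carries no preferred term, severity grade or causality entry.

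**Working it through.** No stated figure needs reproducing. The check compares the two rules and follows one case through the outputs.

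**1. The two rules side by side**

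| Element | Protocol 7.1.3 | Protocol 7.5 |
|---|---|---|
| Default | Leaves out abnormalities without clinical significance | Usually leaves out laboratory abnormalities |
| Mandatory AE when | Intervention needed, or drug interrupted, modified or stopped | Intervention needed, or drug interrupted or stopped |
| Condition on cause | None | Must be independent of the underlying condition |
| Symptomatic and meets AE definition | Record | Record |
| Which governs | Refers to 7.5 for study-specific handling | Silent |

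**2. Where they diverge.** The symptomatic row is the same in both, so that case drops out. What remains is an abnormality that (a) has no signs or symptoms, (b) is attributed to the underlying condition, and (c) needs intervention or interrupts or stops study drug. For this class 7.1.3 says an AE must be recorded, and 7.5 does not require one.

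**3. A worked case.** Study drug is stopped for ALT above 5 times the upper limit (Protocol 3.5). The subject has no symptoms, and the investigator attributes the rise to the underlying condition.

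| Output | AE recorded (7.1.3) | AE not recorded (7.5) |
|---|---|---|
| Treatment-emergent AE tables (SAP 7.1.6) | Counted | Absent |
| Treatment-emergent AEs leading to drug discontinuation (SAP 7.1.6) | Counted | Absent |
| Disposition with reasons (SAP 4.1); Listing 16.2.5.2 | Shown | Shown |
| Graded laboratory tables (SAP 7.2.2) | Shown | Shown |
| Liver-related laboratory table (SAP 7.2.3) | Shown | Shown |

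The loss is confined to the AE outputs.

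**4. Size per subject.** Inputs: about 60 subjects, randomized 2:1 (Protocol 3.2). Presatovir: 60 × 2/3 = 40. Placebo: 60 × 1/3 = 20. Assuming all are dosed and so enter the Safety Analysis Set, one subject missing from a row of an AE table changes that row by:

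- presatovir: 1/40 = 2.5 percentage points;
- placebo: 1/20 = 5 percentage points.

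With k subjects missed the change is k × 2.5 or k × 5 points. The documents give no rate of laboratory-driven stops or interventions and no rate of attribution to the underlying condition, so k cannot be estimated and may be zero.

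**The case against.** The strongest case against is that this is a narrow drafting inconsistency.

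- **Section 7.5 does not forbid recording.** It says abnormalities are usually left out, and 7.1.3 still says they must be recorded. A site that follows 7.1.3 breaches neither section, and 7.1.1 and 7.3 pull the same way. This stands: the loss is possible, not certain.
- **The 7.5 qualifier could mean regardless of the underlying condition.** That would remove most of the conflict. It is the less natural reading, and needing it shows the wording is ambiguous; the differing default sentences would also remain.
- **The stop is visible elsewhere.** This stands. Disposition, listings and laboratory tables show it, a drug given as the intervention during dosing would appear among concomitant medications (SAP 7.4.2), and Protocol 3.5 has the case reviewed with the Medical Monitor. None of these gives the event a preferred term, a grade and a causality assessment.
- **Recording is blinded** (Protocol 5.1). Nothing suggests that one arm would be favoured. Incidence could still be understated and vary by site.

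A reader might also infer more than the documents support:

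- *SAEs would be lost.* Section 7.3 requires every SAE to be reported whatever its cause, and 7.5 is not written as an exception.
- *Section 7.2.1 says causality is judged only after recording.* It sets the criteria for relatedness and says nothing about order.
- *Leaving out drug modification from 7.5 matters.* Protocol 5.3 sets a fixed 14-day schedule and no effect can be shown; the content of Appendix 4 is not visible in the text reviewed.
- *Most abnormalities would be attributed to the transplant, or real stops would be tabulated as none.* No figure supports either. A co-medication effect is also not the underlying condition, so 7.5 does not exempt it.

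**Conclusion.** The concern holds in limited form. Sections 7.1.3 and 7.5 give different mandatory triggers, the section named as study-specific is the narrower one, and no text says which prevails. Under the natural reading of 7.5, an asymptomatic abnormality attributed to the underlying condition need not become an AE even if it needs intervention or stops study drug, which sits against 7.3. Such events can be missing from the treatment-emergent AE tables and from the table of those leading to drug discontinuation, and practice can differ by site.

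The overall size is unknown. The per-subject figures rest on all planned subjects being randomized 2:1 and dosed. The conclusion also assumes that some sites apply 7.5 as written; the eCRF completion guidelines, which were not available, might already settle the matter.

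**What to change.** Reconcile the two sections into one recording rule. In Protocol 7.5, delete the first six words of the passage quoted from it, use the same trigger wording and the same default sentence as 7.1.3, and state which section governs. Attribution to underlying disease then belongs in the causality assessment of 7.2.1, which already names it as an alternative cause. Repeat the rule in the eCRF completion guidelines.

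SAP 7.7 reports that enrolment ran faster than expected, so a protocol edit may come too late to change site practice. If enrolment is complete, compare laboratory-driven study drug stops, interruptions and interventions with the AE records before database finalization, and query sites where no AE was entered. Do this while the blind is in place.

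The cost is a short text edit or one reconciliation listing with a few queries. The downside is a few more AEs to record.
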